### **6.5.3 Bio-sampling and wearables (BioWear) sub-cohort**

Researchers will identify distinct symptom clusters (syndromes) using linked data from CPRD and data collected via the Atom5™ platform. A random sample of up to 300 participants (200 participants with Long COVID, with 50 sampled from each of the four most prevalent Long COVID syndromes, and 50 participants from each of the two control groups) who have previously consented to be contacted for bio-sampling will be identified and invited to take part in the BioWear sub-study. Selected participants will be sent an invitation to participate and the BioWear sub-study PIS via the Atom5™ app, SMS message or by post for those who have expressed having difficulty accessing digital platforms. Those individuals showing an interest in taking part will be contacted by a member of the research team to arrange a date and time for blood and saliva sample collection and to be provided with a wearable device (Garmin Vivosmart4).

### **6.5.4 Co-production cohort**

We will invite individuals who have an interest in treatments for Long COVID to take part in a series of expert consensus and co-production workshops, including:

- People who have experienced Long COVID and their family members, friends, or carers.
- Healthcare professionals.
- Experts in symptoms and potential treatments relevant to Long COVID.
- Regulators.
- Policy makers.

Participants will be recruited from advertisements (distributed in newsletters and social media), word of mouth/known contacts (snowballing), patient support groups (including LongCOVIDSOS), research networks, and Long COVID clinics. Those expressing an interest in participating in the workshops will be given or sent the PIS

electronically or by post prior to the event. In addition, the research team will explain the purpose of the research, the format of the workshop and invite participants to ask questions at the beginning of each workshop.

## **7.0 Consent**

### **7.1 Main study cohort and matched controls**

Participants identified as eligible by their GP and who have shown an interest in taking part in the TLC study will be e-consented via the Aparito Atom5™ app or website, or by telephone. E-consent will comprise completion of the participant consent form on the Atom5™ app or website and using DocuSign to provide an electronic signature. When this is done by telephone, the researcher taking consent will talk through the consent form with the participant and complete the participant's consent form on Atom5™. Participants will have the option to consent to be contacted for future bio-sampling and wearable monitoring devices, if eligible, and other future related studies. Consent forms will be stored within the Aparito Atom5™ platform. For participants who opt to consent by telephone, a copy of the completed consent form will be sent by post by the research nurse. Both online and telephone support for participants will be provided during the consent process.

### **7.2 Bio-sampling and wearable device**

Participants selected for bio-sampling and provision of the Garmin wearable device (TLC BioWear Sub-Study) will be asked to read the PIS and provide e-consent via Atom5™. They will be able to contact the research team to clarify any aspects of the PIS and consent form using the contact details provided in the PIS. Consent will be verified and co-signed by a member of the research team at the bio-sampling appointment. A copy of the consent form will be stored within the Aparito Atom5™ platform. For participants who opt to consent by telephone, a copy of the completed consent form will be provided at the appointment or sent by post. If for any reason it is not possible to take e-consent due to device failure, consent will be taken on paper and the completion of the consent process will be recorded on Atom5™ as soon as possible.

### **7.3 Co-production**

Potential participants will be given or sent the PIS prior to the workshop. Individuals who register to take part in a workshop will be required to provide e-consent via the Aparito Atom5™ platform. E-consent will comprise completion of the participant consent form on the Atom5™ platform website and using DocuSign to provide an electronic signature. If an individual is unable to provide consent electronically, consent will be taken by telephone. When this is done by telephone, the researcher taking consent will talk through the consent form with the participant and complete the participant's consent form on Atom5™.

Consent will include consent to the discussions being audio recorded and the meeting being photographed. Photographs will be taken by a researcher who will be provided with a list of participants who have not consented to their photographs being taken. During in-person workshops, all participants will be wearing name badges which will facilitate identification of participants. Furthermore, the researcher will announce when photographs are being taken.

## 8.0 Study procedures

### 8.1 Population-based representative cohort of individuals with long COVID and matched controls

Eligible individuals who wish to participate will download the Aparito Atom5™ app or visit the website and register using their unique one-time use on-boarding code. They will then be asked to provide electronic consent on the app or website, which includes confirming that participants with a positive SARS CoV-2 RT-PCR result have not been hospitalised within 28 days of being diagnosed with COVID-19. Control participants will be asked if they have ever had COVID-19 to check eligibility for inclusion as a control subject. Once the consent form has been completed, participants will be asked to complete a brief demographic and clinical questionnaire. The questionnaire will ask for the following details: name, sex, date of birth, contact number, postal address, ethnic group, GP address, height, weight, smoking status, pregnancy status, SARS CoV-2 vaccination status, confinement (shielding) status, care home residence, occupation, occupational status (in work, furlough, etc.), and over-the-counter medications used to manage symptoms. Full details of these questions are provided in the appendix (Baseline data collection in Atom5™) and in Table 1.0.

Participants will then be invited to report the presence of established Long COVID symptoms and quality of life using validated tools at monthly intervals for a period of 12 months. At each time point, participants will be asked to confirm their willingness to continue to participate in the study. Those wishing to withdraw will be asked to complete a withdrawal form and advised that any data collected up to that point will need to be retained as it will have been used in aggregated data analyses.

As requested by our PPI group, we will ensure that people who are unable to use the app or website (due to no access to a smartphone or internet connection, patient preference, language, or other requirements) can participate through nurse interview-led appointments (telephone or video conference) with translators as required. Information and contact numbers will be provided on the PIS. Alternative language versions of each PRO will be provided where validated translations exist (see table below) The translated questionnaires are currently being programmed on the app.

	English	Bengali	Polish	Welsh	Punjabi	Gujarati	Urdu
EQ5D5L	X	X	X	X	X	X	X
FACIT F	X	X	X		X	X	X
PHQ-2	X	X	X		X	X	
GAD-2	X		X		X	X	X
PCL-2	X						
modified MRC Dyspnoea Scale	X						
COVID-19 core outcome measure for recovery	X						
SBQ-LC	X						

All participants will be advised where to seek additional support should completion of the PROs raise any concerns regarding their well-being. Proxy-completion will be permitted via the app or website, or via telephone if the participant is unable to complete the PRO and will be documented on the app or website, or via the clinical portal.

Participants will be sent push notification reminders each month to complete the questionnaires on the day completion is due, at 2 days and again at 6 days. Both research personnel and patients will be provided with training resources and telephone support to help minimise missing data. Aparito will provide up to a maximum of two training sessions to the site staff online. A training video will be made available for those that need training after those two sessions. Finally, the site staff will be made aware of the IT support procedures and how to contact Aparito as needed. Aparito will be responsible for providing first line support only to the clinical team via UoB during the duration of the project. Training leaflets outlining how to download and use the app will be provided to staff and patients.

The health service use (primary care consultations, prescriptions, A&E attendances and hospital admissions) and mortality of patients from each Long COVID syndrome will also be described using data from CPRD Aurum and linked data from Hospital Episode Statistics and Office for National Statistics mortality statistics (via CPRD). We aim to use the most up-to-date healthcare data available from CPRD available up to 12 months of follow-up from initial registration on Atom5™.

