**Data-driven analysis to identify distinct Long COVID syndromes (Objective 4, part A)**

We will define distinct symptom clusters (syndromes) using linked data from CPRD and Atom5™ platforms. We will employ clustering algorithms that have been shown to work well in medical settings, with binary and mixed variables: (1) complete linkage hierarchical clustering; (2) probabilistic c-means cluster analysis; (3) density peaked clustering analysis. We will evaluate algorithm performance and the optimal number of clusters (e.g. by internal validation against a holdout dataset using metrics such as Gap statistic and silhouette index).

We will describe the epidemiology of patients within each Long COVID syndrome as well as health service use (primary care consultations, prescriptions, A&E attendances and hospital admissions) and mortality risk and compare these to both sets of matched control patients. We will identify whether Long COVID syndromes are

associated with particular population groups such as BAME groups, patients with long-term conditions, and other vulnerable population groups identified by Public Health England.

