## 6.0. Participant selection and Eligibility

### 6.1 Population-based representative cohort of individuals with COVID-19 (minimum 2000 participants)

#### 6.1.1 Eligibility Criteria

Non-hospitalised individuals with a positive RT-PCR test for SARS-CoV-2 in SGSS data linked to CPRD Aurum. Those from that cohort reporting symptoms associated with COVID-19 at least 12 weeks from the diagnosis will be defined as having Long COVID.

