## **6.3 Matched controls - Group 2 (50 participants)**

### **6.3.1 Eligibility criteria**

Participants taking part in the study who have had a positive SARS CoV-2 RT-PCR test result in SGSS data linked to CPRD but not reporting symptoms on ATOM5™ beyond 12 weeks from the positive RT-PCR test result will comprise Control Group 1. These control participants will be propensity score-matched to participating Long COVID patients.

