## **6.5 Participant identification and recruitment**

6.5.1 Population-based representative cohort of individuals with Long COVID

[figure not shown]
Researchers from The University of Birmingham will use linked data from the Second-Generation Surveillance (SGSS) data that contain SARS CoV-2 positive RT-PCR results to identify patients with confirmed COVID-19 in CPRD Aurum. Using linked Hospital Episode Statistics (HES), the research team will identify and exclude patients who have been hospitalised within 28 days of a positive SARS CoV-2 RT-PCR result or COVID-19 diagnosis).

The list of CPRD Aurum IDs of patients identified as potentially eligible (as above) by the research team will be provided to CPRD. The list of suitable patients will then be uploaded onto the CPRD Interventional Research Services Platform (IRSP). IRSP will generate a unique “username” (Global ID) for each patient on that list, which will be shared with Aparito to assist with verifying participants registering on the Atom5™ app. CPRD will inform participating GP practices that the patient list is available for them to review on by logging onto IRSP. GPs will identify the patients using the corresponding EMIS ID and screen them for their suitability for this study. Researchers at the University of Birmingham will not have access to Patient Identifiable Data until they have consented to participate on Atom5™.

GPs will then invite eligible patients to take part via invitation letters, text message or email which will contain the patient information sheet (PIS) and a username and unique one time password for the Aparito Atom5™ platform. Patients will then log on Atom5™ and provide e-consent (which includes confirming their eligibility) and log data on their symptoms and patient-reported outcomes (PROs). From this data we will identify individuals with prolonged symptoms (>12 weeks) associated with COVID-19, which will form the long COVID cohort.

Participants will be provided a £10 Amazon voucher code via Atom5™ upon completing the baseline questionnaires and a further £10 Amazon voucher upon completing the final study questionnaires at 12 months of follow-up.

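### No date fixes Long COVID or Control Group 2 status, so for late-classified participants classification falls inside the registration-based window for service use and mortality

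*Protocol*

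**What the plan says.** Four parts of the protocol bear on this.

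- **Case definition, Section 6.1.1:** "Those from that cohort reporting symptoms associated with COVID-19 at least 12 weeks from the diagnosis will be defined as having Long COVID". There is a lower bound of 12 weeks, but no visit or date at which the report must be made.
- **Control Group 2, Section 6.3.1:** participants with a positive test but "not reporting symptoms on ATOM5™ beyond 12 weeks from the positive RT-PCR test result". This is equally open-ended.
- **Symptom reports, Section 8.1 and Table 1.0:** collected at baseline and monthly for 12 months. Sections 6.1.1 to 6.1.3 set no minimum interval between the positive test and registration.
- **Outcomes:** Section 8.1 will describe consultations, prescriptions, A&E attendances, admissions and deaths by syndrome, with data "available up to 12 months of follow-up from initial registration on" Atom5. Section 5.0 (WP2, Objective 4 part A) will describe service use "mortality risk and compare these to both sets of matched control patients".

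Two places point towards early classification. Section 6.5.1, after describing log-on, e-consent and symptom logging, says "From this data we will identify individuals with prolonged symptoms (>12 weeks) associated with COVID-19". Section 11.1 invites the syndrome samples and controls for bio-sampling 3 months after enrolment. Control Group 1 is defined from primary care and laboratory records (Section 6.2).

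**The concern.** Follow-up for the outcomes is measured from registration, while the reports that separate two of the compared groups can arrive at any monthly assessment afterwards. Followed literally, someone who is silent at baseline and reports qualifying symptoms some months later stops meeting the Control Group 2 definition and becomes a Long COVID case. The months already elapsed then sit in the Long COVID group, although a death in those months would have prevented that classification. Control Group 2 is in turn reduced to people selected by what they did not report later.

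At stake is the service-use and mortality comparison in WP2. An illness episode close to the qualifying report can both produce a consultation and move the person into the Long COVID group. For mortality, part of a case's follow-up is free of deaths by construction.

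**Working it through.** The protocol gives no rate, sample size or power for service use or mortality, so there is no stated figure to reproduce. The check sets the definitions against three kinds of participant and then illustrates the size under stated assumptions.

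**Who is affected**

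- Past 12 weeks at registration and reporting symptoms at baseline: classified when follow-up starts. Essentially no immortal time.
- Past 12 weeks at registration, silent at baseline, first qualifying report d months later: d months of the window precede classification.
- Registered less than 12 weeks after the test: status cannot exist when follow-up starts. In the extreme case of registration on the day of the test, 84 days or 84/30.4375 = 2.76 months pass first.

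**Inputs**

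- Outcome window of 12 months (Section 8.1).
- Long COVID share of the COVID-19 cohort, s: 500/2000 = 0.25 or 750/2000 = 0.375 (Section 5.0, WP1, Objective 1).
- Assumed, not in the protocol: the delay d, a constant low death rate, a true rate ratio of 1, and, for the ratios below, every Long COVID case classified at the same d.

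**Formulas**

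- Immortal share of a case's window = d/12.
- Rule A, deaths before classification fall to Control Group 2: ratio = [(12 − d)/12] / {[(1 − s)·12 + s·d] / [(1 − s)·12]}.
- Rule B, those deaths are dropped from the Long COVID group only: ratio = (12 − d)/12.

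For d = 3 and s = 0.25, Rule A gives 0.75 / [(9 + 0.75)/9] = 0.75/1.083 = 0.69.

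| d (months) | Immortal share | Rule A, s = 0.25 | Rule A, s = 0.375 | Rule B |
|---|---|---|---|---|
| 0 | 0% | 1.00 | 1.00 | 1.00 |
| 1 | 8% | 0.89 | 0.87 | 0.92 |
| 2.76 | 23% | 0.72 | 0.68 | 0.77 |
| 3 | 25% | 0.69 | 0.65 | 0.75 |

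**Other allocation rules**

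Suppose Control Group 2 membership also needs c months of silent reports and earlier deaths are dropped from both groups. The ratio is then (12 − d)/(12 − c). With c = d it is 1.00; with d = 1 and c = 3 it is 11/9 = 1.22. The sign therefore follows from a rule that the protocol does not state.

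**Dilution**

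If only a fraction f of cases is classified late, the immortal share of the whole Long COVID group's window is f·d/12. The protocol gives no basis for f.

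**With a common landmark**

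If follow-up starts at the classification assessment in both Long COVID and Control Group 2, no counted time precedes classification, and the ratio is 1.00 under the same assumptions.

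**The case against.** The strongest reply is that the protocol is silent rather than wrong. No section says that status accrues over the whole year. Section 6.5.1 reads naturally as identification from the first data logged, and Section 11.1 implies that the sampled participants have a status by about month 3. Section 8.1 states where the data window ends and only implies where counting starts. The start of follow-up is often left to a statistical analysis plan, and the outcomes are mainly to be described, with no model named.

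Much of this stands. A reader might infer that every Long COVID case carries immortal time, or that status is settled only at month 12. The documents do not support either. Nor do they make Control Group 1 depend on symptom reports, so in that comparison only the Long COVID side can carry immortal time.

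What does not stand is that nothing needs fixing. The open-ended definitions and the registration-anchored window are the protocol's own. Section 6.5.1 names no visit, Section 11.1 concerns bio-sampling invitations only, and classification at month 3 with follow-up from registration still leaves 3 of 12 months immortal for a case classified then. Only classification at baseline avoids the overlap, and it is impossible for anyone registering before week 12.

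It can also be said that consultations in symptomatic weeks are a genuine part of the burden. That is fair for a description within a syndrome. It does not cover the contrast with a Control Group 2 chosen by the absence of later reports.

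**Conclusion.** The point holds in a limited form. For participants registering less than 12 weeks after their test, or first reporting qualifying symptoms after baseline, group membership is decided inside the period over which service use and deaths are followed. For those past 12 weeks and classified at baseline the problem is practically nil.

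The size for this study cannot be derived from the protocol, because neither the delay nor the fraction classified late is given. Under assumed delays of 1 to 3 months, 8% to 25% of a late-classified case's window is immortal.

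A reader might infer that Long COVID mortality must be biased downwards. That follows if early deaths fall to Control Group 2 or are dropped from the Long COVID group alone, but other allocation rules give no bias or the opposite sign. A reader might also expect a definite inflation of service use. Overlap makes some inflation plausible against Control Group 2, but any ratio would rest on illness and consultation rates that the protocol does not contain, and on a case definition looser than its persistent-symptom one.

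**What to change.** Add wording to the outcome paragraph in Section 8.1, with a cross-reference from WP2 in Section 5.0, for the service-use and mortality comparison:

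- Set Long COVID or Control Group 2 status once, at the first completed questionnaire at least 12 weeks after the positive test. This is the baseline questionnaire for those already past 12 weeks. Use baseline for Control Group 1.
- Count service use and deaths only from that date in all groups, using person-time because windows will differ in length.
- Report how many COVID-19 participants die or leave before their landmark; they enter neither Long COVID nor Control Group 2 in this comparison.
- Analyse later changes of status as time-varying in a sensitivity analysis.

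No new data are needed. There are two costs. Weeks before the landmark are lost for early enrollers; at the extreme of registration on the day of the test, about 12 − 2.76 = 9.24 months of the window remain. And because symptoms can relapse and remit (Section 1.0) while the SBQ-LC asks about the last 7 days (Section 9.1), some cases in remission at the landmark will count as controls in the main comparison. The time-varying analysis addresses that misclassification and should be reported beside the main result.

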## **8.2 Clinical support**

The majority of symptoms of long COVID, while potentially debilitating, are not associated with acute medical emergencies. However, some symptoms of long COVID can be distressing, and also can mirror symptoms of potentially dangerous medical conditions, such as a blood clot or stroke. The TLC study cannot provide overarching medical care for participants, and their care remains with their usual care providers.

To provide support and guidance, access to nurse-led clinical support (during usual working hours of 8am - 5pm, Monday-Friday (excluding public holidays)) with oversight by a consultant respiratory physician ([name]) will be provided for participants reporting severe symptoms on Atom5™. [name] will be mentoring and supporting the nurses, providing medical guidance when needed by answering the nurses queries and ensuring signposting to appropriate medical services, as needed. This might include reviewing questionnaire answers from participants, speaking to participants should any severe symptoms be flagged or should the participant wish to speak to a doctor involved in the TLC study, or speaking to the participant's usual medical practitioner to discuss responses to the questionnaires. [name] can only provide signposting advice (including asking the participant to present to hospital for an emergency review if needed), to ensure appropriate safety netting for the participant, and cannot provide medical treatments or further investigation, as the participant will remain under the care of their usual medical practitioner.

Should participants be concerned about their symptoms or experience a sudden deterioration in their symptoms, they will be encouraged to discuss this with their GP, call 111 or 999, depending on the severity of their symptoms, as per usual standard of care practices and as advised by the medically qualified support team. This will be explained on the PIS. The nurse-led support team can signpost to medical assistance, but will not be able to provide direct medical care or aid.

GPs or the participants' usual care team will not be routinely informed about the results of the research or the data collected. However, Atom5™ will be configured to report the recording of severe symptoms to the research nurse via the Atom5™ clinical portal. The research nurse will then contact the participant to assess the level of support needed and signpost to relevant services and information or escalated to the consultant physician for further advice if needed. The advice given may include a recommendation for the participant to contact their GP or NHS 111 to discuss their symptoms or seek more urgent help by contacting 999. The participant's GP will only be contacted if the participant cannot be reached after three attempts over the

course of 24 hours and the participant has provided their GP details. We will seek specific consent for these actions. Any verbal contact with the participant or GP will be followed by a written letter.

Participants will be advised in the PIS and in the Atom5™ app and website that the data will not routinely be seen by their GP or usual care team. If they are concerned about symptoms or well-being they should dial 111. In an emergency they should dial 999. They will also be provided with the link to the NHS Your COVID Recovery website (<https://www.yourcovidrecovery.nhs.uk>). Participants reporting symptoms of urgent clinical concern will receive the following notification on Atom5™: “You have reported symptoms that may require urgent follow-up. We recommend you contact 111 to seek further advice. In an emergency dial 999.”

